Immunogenicity: Serum levels of anti-AG-73305 antibodies (using binding and neutralizing antibody assays, if available).

Study Population: Approximately 25, adult male or female patients with center involving DME in the study eye will participate in the study, including a sentinel patient in each of 4 dose cohorts.

Phase: 2a

Description of Sites: Approximately 8 sites in the United States will enroll patients.

Description of Study Treatment: AG-73305 is a humanized IgG1 Fc-fusion protein that targets vascular endothelial growth factors, placental growth factors and integrins. AG-73305 is a clear solution formulated in a 40 mg/mL concentration for intravitreal injection. Ascending doses of a single injection of AG-73305 will be assigned by cohort to 0.5, 1, 2, and 4 mg or until the maximally tolerated (or maximum administered) dose has been reached (see Table 1).

Rescue Medication will be standard-of-care anti-vascular endothelial growth factor (VEGF) administered by IVT in the study eye. Rescue medication is allowed at the Week 4 visit or later in patients meeting any of the following criteria:

- Loss of > 10 ETDRS letters from a previous best study visit with worsening of intraretinal or subretinal fluid observed by SD-OCT and judged by the Investigator to be the cause of the BCVA loss.
- Loss of > 5 ETDRS letters at 2 consecutive visits (one can be unscheduled) from a previous best study visit due to worsening of DME.
- An increase in CST > 75 μ m from a previous best study visit which remains consistently > 75 μ m from the previous best study in two consecutive visits, as assessed by SD-OCT.

The later visit can be an unscheduled visit if determined to be necessary by the Investigator.

- An increase in CST $> 50 \mu\text{m}$ from a previous best study visit, as assessed by SD-OCT and a loss of > 5 ETDRS letters, which remains consistently $> 50 \mu\text{m}$ and loss > 5 ETDRS letters from the previous best study in two consecutive visits. The later visit can be an unscheduled visit if determined to be necessary by the Investigator.
- Progression of or worsening of proliferative diabetic retinopathy.

Patients will be followed for at least 4 weeks after Rescue medication administration or through Week 12, whichever is greater.

Table 1: Summary of Open-label Cohorts and Dosing

Dose (mg)	Stock Vial Concentration (mg/mL)	Dilution Requirement	Volume to be Injected (mL)
0.5	40	1:1 with diluent	0.025
1	40	None	0.025
2	40	None	0.050
4	40	None	0.100

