9.7.1. Statistical and Analytical Plans

General Conventions

Summary statistics for the data collected during this study will be presented to give a general description of the patients studied. Data from all sites will be combined in the computation of these descriptive summaries. Categorical variables will be summarized by the frequency and percentage of patients in each category. Continuous variables will be summarized using N, mean, standard deviation (SD), median, minimum, and maximum values.

Number of patients, minimums, and maximums will be calculated to the same number of decimal places as the source data. Means, medians, standard deviations, and quartiles will be calculated to one more decimal place than the source data. Percentages will be calculated to the nearest one decimal place. Zero count cells will be displayed as “0” with percentage of (0%). Unless otherwise noted, summaries will be performed by the treatment group and presented in the order of: AG-73305, 0.5 mg; AG-73305, 1 mg; AG-73305, 2 mg; AG-73305, 4 mg.

Baseline values will be defined as the last measurement prior to dosing of study medication. Ocular measurements will use the most recent measurement for each eye.

Numeric laboratory, pharmacokinetic, and immunogenicity data may be recorded at limits of detection (with a ‘<’ or ‘>’ sign, e.g., < 0.1 or > 0.1). To summarize laboratory data, the original value will be converted to one unit less or more at the level of measured precision (e.g. 0.4 in the case of < 0.5 and to 0.6 in the case of > 0.5). For pharmacokinetic data, for Time = 0 (predose), any result that is below the level of quantitation (BLQ) is set to zero; all other timepoints are set to missing for any computations. For immunogenicity, any titer < Value (a negative result) is set to zero. Summary tables for immunogenicity titer will not include these negative results.

The actual values will be presented in the data listings.

All data collected in this study will be presented in individual patient data listings for all patients.

Computations for all results will be performed using SAS (Version 9.4, SAS/STAT 15.2) computer software package (SAS Institute, Inc, 2013, 2020), unless otherwise specified.

Strata and Covariates

Not applicable.

Subgroups

Not applicable.

Multiplicity

Not applicable.

Missing Data and Outliers

Every attempt will be made to capture all study data. All analyses will utilize observed data only.

Visit Windows

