9.7.1.1. Analysis Populations

9.7.1.1.1. Populations

The Full Analysis Set will include all patients who received at least one dose of investigational product as indicated on the dosing record. Patients will be analyzed in the group according to the treatment received. All efficacy and safety variables will be analyzed using the Full Analysis Set and only observed data will be included.

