9.7.1.5. Analysis of Efficacy

Summary descriptive statistics will be presented for all study visits at which efficacy data are collected. Efficacy analyses will be presented by cohort for the study eye using the FAS population. Data for efficacy assessments for the non-study eye will be provided in listings.

All efficacy data will be censored (set to missing) on or after the earliest instance of rescue therapy when summarized in tables. All data will be presented in listings.

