9.7.1.5.1. Primary Efficacy Analysis

The key efficacy measure is best-corrected visual acuity score of the study eye using the ETDRS as assessed by certified Investigator or designee. The endpoint is the change from baseline in ETDRS letters at Week 4, so scores from Day 1 and Week 4 will be analyzed. Final scores will be calculated as Week 4 minus Day 1 BCVA letter counts. A positive result will indicate more letters gained following AG-73305 injection, while a negative score indicates worsening of vision. Observed and change from baseline in BCVA letter count at other visits will be summarized in a similar fashion to the key efficacy measure.

In addition, change from baseline in BCVA letter count as measured by ETDRS at each visit and the proportion of study eyes with ≥ 5 , ≥ 10 , and ≥ 15 BCVA letter increase from baseline will be analyzed.

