9.7.1.6.4. Slit Lamp Biomicroscopy

The frequency and percentage of patients with observed values of each categorical response or grade as well as the categorical shift from baseline at each post-baseline visit will be tabulated at each scheduled visit for both eyes. The percentages of patients with observed values of each categorical response will be calculated based on the number of patients at each visit in each treatment group of the FAS. Percentages for categorical shifts from baseline will be based on the number of patients with baseline and post-baseline values at each visit in each treatment group.

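### The 5-, 10- and 15-letter responder proportions are labelled Full Analysis Set but leave out rescued eyes, so they are inflated relative to counting rescue as non-response and are not comparable between cohorts with different rescue use

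*SAP*

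**What the plan says.** Three SAP rules act together.

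- **Rescue (9.7.1.5):** "All efficacy data will be censored (set to missing) on or after the earliest instance of rescue therapy when summarized in tables".
- **Missing data (9.7.1, Missing Data and Outliers):** "All analyses will utilize observed data only". Section 9.7.1.1.1 repeats this for the analysis set: "All efficacy and safety variables will be analyzed using the Full Analysis Set and only observed data will be included".
- **Endpoint (9.7.1.5.1):** besides the Week 4 mean change, the SAP plans "change from baseline in BCVA letter count as measured by ETDRS at each visit and the proportion of study eyes with" gains of at least 5, 10 and 15 letters. It gives no denominator and does not say how a rescued eye is classified.

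Elsewhere the SAP does write denominators. Slit-lamp percentages, for example, are "calculated based on the number of patients at each visit in each treatment group of the FAS" (9.7.1.6.4).

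On rescue itself, both synopses say: "Rescue medication is allowed at the Week 4 visit or later in patients meeting any of the following criteria". Of the five criteria, four rest on letter loss, on an increase in central subfield thickness (CST), or on both. The fifth is progression or worsening of proliferative retinopathy. Letter and CST changes are measured from the best earlier study visit, for example: "Loss of > 5 ETDRS letters at 2 consecutive visits (one can be unscheduled) from a previous best study visit".

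Section 9.7.1.5.2 reports rescue separately, by Kaplan-Meier time to rescue, use by visit and reasons.

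**The concern.** A value that is set to missing under an observed-only rule does not enter the table. The rescued eye is then neither a responder nor a non-responder, and the proportion describes only eyes that have not needed rescue. Most rescue criteria reflect loss of effect, so the removal is informative.

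Duration of effect is a stated objective, and one of the two study hypotheses is that at least one dose shows some clinical benefit. Late-visit responder rates bear on both. With 3 to 8 patients per cohort (SAP 9.7.2), a few rescues can dominate the rate. Two doses with the same number of unrescued responders can then show very different percentages only because one needed more rescue.

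**Working it through.** **The plan's own figure.** The only calculated figures are in SAP Table 2, from 1-(1-p)^n. All 24 cells reproduce; for example, 1-0.95^8 = 0.337. They concern dose-limiting toxicities and serious adverse events. The plan states no responder or rescue rate, so the counts below are assumed.

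**Step 1: effect of the denominator.** Let n be treated eyes in a cohort, k the eyes whose value is removed because of rescue, and r the responders among the rest. Assume no other missing data.

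- Observed-only rate: r/(n-k).
- Rate with rescue as non-response: r/n.
- Ratio: n/(n-k), which is never below 1.

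| n = 8, r = 3 | Observed-only | Rescue as non-response | Ratio |
|---|---|---|---|
| k = 0 | 3/8 = 37.5% | 37.5% | 1.00 |
| k = 2 | 3/6 = 50.0% | 37.5% | 1.33 |
| k = 3 | 3/5 = 60.0% | 37.5% | 1.60 |
| k = 4 | 3/4 = 75.0% | 37.5% | 2.00 |

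Cohorts with no rescue and with four rescues would be reported at 37.5% and 75.0%, although each has 3 unrescued responders among 8 treated.

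**Step 2: does the rate rise as eyes fail?** Let R eyes be responders before rescue, and let q of the k rescued eyes be among them. The observed-only rate moves from R/n to (R-q)/(n-k), and it rises only if q/k < R/n. With n = 8, R = 4 (50%) and k = 3:

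- q = 0: 4/5 = 80%
- q = 1: 3/5 = 60%
- q = 2: 2/5 = 40%
- q = 3: 1/5 = 20%

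The cases q > 0 are possible. An eye that peaked at +12 letters and then lost 6 at two consecutive visits meets the letter threshold for rescue, yet stands at 12 - 6 = +6 against baseline.

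**Step 3: illustrative simulation.** All inputs are assumed:

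- Mean gain of 6 letters at Week 4 (SD 5), half of that at Week 1, waning linearly to zero at Week 24.
- Drift SD 2 per visit; measurement SD 3, including at baseline. The less noisy case uses 1 and 2.
- Rescue from Week 4 whenever loss from best exceeds 10 letters, or exceeds 5 at two consecutive visits.
- 200,000 simulated patients.

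| Week 24, gain of at least 5 letters | Noisier case | Less noise |
|---|---|---|
| Observed-only | 36-45% | 13-15% |
| All eyes, had none been rescued | 23% | 10% |
| Rescue as non-response | 12-13% | 6-7% |

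Ranges cover keeping or dropping a value measured on the day of rescue. In the noisier case the observed-only rate falls over time, from about 55-58% at Week 4, but more slowly than the rate that counts rescue as non-response. The mean change in unrescued eyes at Week 24 is about +2.8 to +4.4 letters where the true mean is 0, so the mean-change table is selected in the same way.

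**The case against.** **The study is descriptive and rescue is already visible.** This is an open-label dose-escalation study whose cohort size has no power basis. The key measure is mean change at Week 4, and the proportions are additional. Kaplan-Meier curves, rescue by visit and listings are planned, and continuous summaries print N. This limits the stakes. It does not correct a responder table that is described as FAS but covers a selected subset, nor does it make cohorts comparable.

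**The denominator is inferred.** It is not written for this endpoint; it follows from the censoring rule together with the observed-only rule. If the sponsor intended the full FAS count, rescued eyes would already count as non-responders, but the SAP would still need to say so.

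**Rescue as failure is only one estimand.** This stands. A summary of unrescued eyes is legitimate if labelled as such. Part of the simulated gap is the change of definition: counting rescue as failure puts the rate (12-13%) below the rate in all eyes (23%). The distance from 36-45% down to 12-13% should not all be called bias.

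**The simulated rescue rate is high.** This also stands. Rescue is permitted, not required. The 10-letter criterion needs worsening fluid judged to be the cause, and the 5-letter criterion needs worsening of the macular edema. The model triggers on letters alone and removes about 63-74% of eyes by Week 24 in the noisier case.

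**A stronger reading to avoid.** A reader might infer that the reported rate climbs as more eyes fail. The documents do not support that. No criterion uses change from baseline, so responders can be among those removed, and the rate can fall (Step 2).

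**Conclusion.** The concern holds in this form. As the SAP is written, rescued eyes leave both parts of the 5-, 10- and 15-letter proportions. Relative to counting rescue as non-response, the reported rate is n/(n-k) times as high and never lower, provided the same values are removed in both and nothing else is missing. In a cohort of 8, that is a third higher with two rescues and double with four. Later-visit rates therefore cannot be compared between cohorts with different rescue use.

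The direction is certain only against that comparator. Inflation against all eyes had none been rescued appears in the simulation but rests on its assumptions. Actual size is unknown, because the documents give no rescue or response rates.

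Week 4 is largely spared, since rescue starts at that visit. It is not immune: the censoring applies on or after rescue, so it can delete a Week 4 value measured on the day rescue is given.

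**What to change.** In SAP 9.7.1.5.1:

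1. Report the 5-, 10- and 15-letter proportions at each visit with all FAS patients in the cohort as denominator, counting eyes rescued before that visit as non-responders.
2. Beside this, show the observed-case rate, labelled 'eyes not yet rescued'.
3. Print the number rescued to date and n unrescued/N in this table and in the mean-change table.
4. State whether a value measured on the day of rescue, before rescue is given, is kept, and apply the same choice to both rates.

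Showing both rates avoids having to settle on one estimand. The cost is SAP wording and table programming. No new data are needed, because counting rescue as non-response requires no measurement after rescue. The drawback for the sponsor is that late-visit responder rates will look less favourable.

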#### **Response Measures:**

##### *Safety assessments:*

- Adverse Events (AEs)
- ETDRS BCVA
- Intraocular pressure (IOP)
- Slit lamp biomicroscopy
- Dilated fundus exam (DFE)
- Crystalline lens assessment using AREDS scale
- Post-injection assessment
- Laboratory evaluation (hematology, serum chemistry and urinalysis)
- Electrocardiogram (ECG)
- Vital signs
- Physical examination
- Pregnancy test

*Efficacy assessments:*

- Improvements in ETDRS BCVA
- SD-OCT (Heidelberg Spectralis, dense scan) as measured by Central Reading Center (CRC)
  - Central subfield thickness (CST)
  - Ellipsoid zone (EZ)
  - External limiting membrane (ELM)
  - Intraretinal and subretinal fluid
  - Posterior vitreous detachment
- OCT-A as measured by CRC
  - Foveal avascular zone (FAZ)
  - Foveal capillary density (CD) (superficial and deep capillary plexuses)
- Diabetic retinopathy severity score (DRSS) assessed via color fundus photography
- Time to rescue medication

*Pharmacokinetics:* Plasma concentrations of AG-73305.

*Immunogenicity:* Serum levels of anti-AG-73305 antibodies (using binding and neutralizing antibody assays, if available).

**Study Population:** Approximately 25, adult male or female patients with center involving DME in the study eye will participate in the study, including a sentinel patient in each of 4 dose cohorts (see [Figure 1](#)).

**Phase:** 2a

**Description of Sites:** Approximately 8 sites in the United States will enroll patients.

**Description of Study Treatment:** AG-73305 is a humanized IgG1 Fc-fusion protein that targets vascular endothelial growth factors, placental growth factors and integrins. AG-73305 is a clear solution formulated in a 40 mg/mL concentration for intravitreal injection. Ascending doses of a single injection of AG-73305 will be assigned by cohort to 0.5, 1, 2, and 4 mg or until the maximally tolerated (or maximum administered) dose has been reached (see [Table 1](#)).

**Rescue Medication** will be standard-of-care anti-vascular endothelial growth factor (VEGF) administered by IVT in the study eye. Rescue medication is allowed at the Week 4 visit or later in patients meeting any of the following criteria:

- Loss of > 10 ETDRS letters from a previous best study visit with worsening of intraretinal or subretinal fluid observed by SD-OCT and judged by the Investigator to be the cause of the BCVA loss.

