9.5.1.2.2. Medical and Surgical History

9.5.1.2.3. Ocular and non-ocular medical and surgical history will be collected at the Screening Visit. Prior and Concomitant Medications

Previous history of anti-VEGF IVT treatment for DME should be collected as detailed as possible, minimally for the last three years from baseline.

Details of all medications (other than those intended to treat the study patient's DME), therapies and supplements administered within 3 months prior to Screening Visit until the end of the study will be recorded in the electronic case report form (eCRF).

Permissible, prohibited, and rescue medications are outlined in the protocol Sections 6.5.1 – 6.5.3.

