9.5.1.3.2. Secondary Efficacy Assessments

Dilated color fundus photography will be performed OU at the Baseline Visit, in the SE at Week 4, and OU at Week 24 to assess diabetic retinopathy severity score (DRSS).

Spectral Domain Optical Coherence Tomography (SD-OCT) will be performed OU at each in-clinic visit (Heidelberg Spectralis, dense scan). SD-OCT will assess central subfield thickness (CST), ellipsoid zone (EZ), external limiting membrane (ELM), intraretinal and subretinal fluid volume, and posterior vitreous detachment.

OCT Angiography (OCT-A) will be performed OU at the Baseline Visit, in the SE at Weeks 4 and 24, and OU at the visit when Rescue treatment is given. OCT-A will assess foveal avascular zone (FAZ) and foveal capillary density (CD) (superficial and deep capillary plexuses).

Color fundus photos and SD-OCT and OCT-A images will be submitted to a central reading center for grading.

Time to rescue medication will be assessed. Rescue medication will be standard-of-care anti-vascular endothelial growth factor (VEGF) administered by intravitreal injection (IVT) in the

study eye. Rescue medication is allowed at the Week 4 visit or later in patients meeting any of the criteria outlined in the protocol Section 6.5.3.

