9.7.1.5.2. Secondary Efficacy Analyses

Observed and change from baseline in CST as measured by SD-OCT at Week 1, 4, 8, 12, 16, 20 and 24 will be presented. A change from baseline in CST will indicate a positive response if the treatment difference is < 0 . Observed and change in intraretinal and subretinal fluid volumes, ELM and EZ by SD-OCT at each visit will also be presented. The presence of posterior vitreous detachment will be summarized by frequency and percentage.

Observed and change from baseline in FAZ and CD of the superficial and the deep capillary plexuses will be presented, as measured by OCT-A at the Baseline Visit, Week 4, and Week 24.

Observed and change from baseline in DRSS will be presented, assessed via color fundus photography at the Baseline Visit, Week 4, and Week 24.

Time from Day 1/Baseline to receipt of rescue medication in the study eye will be analyzed using Kaplan-Meier time-to-event analyses. Follow-up is measured to the earliest instance of receipt of rescue therapy in the study eye for patients receiving rescue therapy. Otherwise, patients are censored at the date they complete or discontinue the study. In addition, reasons for rescue and use of rescue medication by visit will be summarized by frequency and percentage. Rescue will be included at Visit X if the date rescue is provided is on or after Visit X and before Visit X + 1.

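### The efficacy set-to-missing rule and the time-to-rescue event both depend on intravitreal anti-VEGF rescue, so a study eye given laser, steroid or intraocular surgery is covered by neither

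*SAP*

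**What the plan says.** **What rescue is.** The synopsis reproduced in the SAP defines it: "Rescue Medication will be standard-of-care anti-vascular endothelial growth factor (VEGF) administered by IVT in the study eye". The protocol synopsis and SAP 9.5.1.3.2 say the same. A separate sentence gives timing and conditions: "Rescue medication is allowed at the Week 4 visit or later in patients meeting any of the following criteria". One listed criterion is "Progression of or worsening of proliferative diabetic retinopathy".

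**How efficacy data are handled.** SAP 9.7.1.5: "All efficacy data will be censored (set to missing) on or after the earliest instance of rescue therapy when summarized in tables". No other treatment triggers the rule.

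**How time to rescue is handled.** SAP 9.7.1.5.2: "Follow-up is measured to the earliest instance of receipt of rescue therapy in the study eye for patients receiving rescue therapy". For everyone else: "Otherwise, patients are censored at the date they complete or discontinue the study".

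**Other categories of treatment.** The medication text in SAP 9.5.1.2 separates rescue from prohibited treatment: "Permissible, prohibited, and rescue medications are outlined in the protocol Sections 6.5.1 – 6.5.3". Those protocol sections are not part of the protocol text at hand.

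**Analysis set.** SAP 9.7.1.1.1 defines only the Full Analysis Set, with observed data. SAP 9.7.1.2 tabulates major deviations in that set and excludes nothing because of them.

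**The concern.** By setting values to missing after rescue, the SAP accepts that what is measured after another treatment is no longer an AG-73305 result. That reasoning applies equally to laser, a steroid or intraocular surgery in the study eye, but the rule stops at anti-VEGF. The gap can open within the plan's own rescue criteria: an eye may qualify through proliferative retinopathy, receive laser, and still not count as rescued.

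Duration of effect is a stated objective, and time to rescue bears directly on it. There is no control arm, and cohorts have 3 to 8 patients, so a single misclassified eye shows in the result.

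**Working it through.** **Step 1. Follow one eye through the rules.** Take a study eye that receives each treatment after dosing, with the patient staying in the study and receiving no later anti-VEGF.

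| Treatment in the study eye | Set to missing (9.7.1.5)? | Event (9.7.1.5.2)? |
|---|---|---|
| Anti-VEGF, Week 4 or later, criterion met | Yes | Yes |
| Anti-VEGF before Week 4 or without a criterion met | Ambiguous | Ambiguous |
| Laser or steroid for DME or retinopathy | No | No; censored at study completion |
| Intraocular surgery | No | No; censored at study completion |

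The first row shows that the plan works as intended for protocol rescue. The last two rows are the gap.

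**Step 2. Size on the rescue-free proportion.** The plan gives no figure on this point, so the inputs are the cohort sizes in SAP 9.7.2 (3, 6 and 8) plus stated assumptions: no early exits, and one eye given a non-anti-VEGF treatment and never rescued. At a single event time the Kaplan-Meier estimate is S = 1 - d/n. Counting the eye as an event lowers S by 1/n:

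- n = 3: 1/3 = 33.3 percentage points
- n = 6: 1/6 = 16.7 percentage points
- n = 8: 1/8 = 12.5 percentage points

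Two worked cases (event counts assumed):

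- n = 6, two eyes rescued at Week 8 and a third given other treatment then: 1 - 2/6 = 4/6 = 67% as written; 1 - 3/6 = 3/6 = 50% if counted.
- n = 8, three eyes rescued and a fourth given other treatment: 5/8 = 62.5% as written; 4/8 = 50% if counted.

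**Step 3. Effect on mean BCVA change.** Let x be the treated eye's change at a later visit and m the mean of the other n - 1 eyes. As written the mean is ((n - 1)m + x)/n. With the eye set to missing it is m. The difference, m minus the mean as written, is (m - x)/n, so its sign depends on whether x lies above or below m. With n = 6 and five eyes at +6 (all values assumed):

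- Sixth eye at +12 after the other treatment: (30 + 12)/6 = 7.0 as written; 30/5 = 6.0 if set to missing. The mean falls by 1.0.
- Sixth eye at -5, then +3 after the other treatment: (30 + 3)/6 = 5.5 as written; 30/5 = 6.0 if set to missing. The mean rises by 0.5. Had that eye stayed untreated, the mean would have been (30 - 5)/6 = 4.2.

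**Step 4. Chance that it arises.** The documents give no rate. SAP Table 2 uses 1 - (1 - p)^n, and its 5% row reproduces: 0.143, 0.265 and 0.337 for n = 3, 6 and 8. The same formula with an assumed share of patients given such treatment:

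| Assumed share | n = 3 | n = 6 | n = 8 | All 25 patients |
|---|---|---|---|---|
| 2% | 0.059 | 0.114 | 0.149 | 0.397 |
| 5% | 0.143 | 0.265 | 0.337 | 0.723 |
| 10% | 0.271 | 0.469 | 0.570 | 0.928 |

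**The case against.** The study is open-label and descriptive, with no powered test. Its key endpoint is at Week 4. Study-eye medications and major deviations are tabulated, and all data are listed, so in cohorts this small a reader could find such an eye. Protocol Sections 6.5.1–6.5.3 might also require withdrawal after a prohibited treatment.

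Much of this stands as a limit on severity. Tracing an eye in a listing does not correct the tables, however. Traceability is also less certain than it looks: the medication text in SAP 9.5.1.2 exempts drugs meant for the patient's DME from its general recording requirement. If withdrawal is required, later values stop and the patient is censored at exit, but the other treatment still does not become an event.

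Four stronger readings are tempting, and the documents do not support them:

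- *That early or off-criteria anti-VEGF certainly escapes both rules.* The definition says what rescue is, and the separate sentence says when it is allowed. Such an injection can be read as already covered. The text is ambiguous.
- *That a patient who leaves for lack of effect is carried to Week 24 as rescue-free.* SAP 9.7.1.5.2 censors that patient at discontinuation, so the patient leaves the risk set. Whether such censoring is informative is a separate question.
- *That the gap always inflates mean BCVA.* An assumed 8-letter gain in one of six eyes, 8/6 = 1.3 letters, compares the eye with its own untreated course. It does not compare the mean as written with the mean after the eye is set to missing; Step 3 shows that difference can have either sign.
- *That the Week 4 result is broadly compromised.* Only treatment before the Week 4 assessment can affect it.

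**Conclusion.** The gap is real for non-anti-VEGF treatment of DME or retinopathy and for intraocular surgery in the study eye. Followed as written, the SAP keeps later BCVA, CST and DRSS values in the cohort summaries and counts the eye as rescue-free. One such eye moves a cohort's rescue-free proportion by 12.5 to 33.3 percentage points, assuming the patient stays in the study, is not later rescued, and no one exits early. The effect on mean BCVA has no fixed direction. The exposure lies in visits after Week 4 and in the duration-of-effect objective. How often such treatment occurs is unknown, and the unseen protocol sections on prohibited and rescue medication could narrow the problem. It is worth correcting because the change is small and affects only the analysis.

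**What to change.** The change is to the analysis text only; who may be treated, with what and when stays as it is.

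1. **SAP 9.7.1.5.** Set study-eye efficacy values to missing from the first of: any study-eye anti-VEGF, whether or not the rescue criteria were met; any other DME or diabetic retinopathy treatment apart from AG-73305; or intraocular surgery.
2. **SAP 9.7.1.5.2.** Keep the rescue-only curve that the protocol names, and state how it classifies anti-VEGF given early or outside the criteria. Beside it, show a Kaplan-Meier curve of time to first additional study-eye DME or retinopathy treatment, rescue or not. Surgery unrelated to DME or retinopathy should not count as an event.
3. **Data source.** Identify cases from both the Concomitant Medication and the Concurrent Procedures records, which the schedule collects at every visit. Confirm that the eCRF captures non-rescue drugs given for DME.

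The cost is SAP wording, one derived flag, one extra display and the eCRF check. The downside is a few more missing values. These can remove poorly responding eyes and so flatter the means, which should therefore be read together with the time-to-treatment curve.
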